12.4 Replacement of Subjects

Subjects who withdraw from the study will not be replaced. We will conduct our analyses on an intent-to-treat basis and will rely on multiple methods (including censoring and imputation) to examine the sensitivity of our findings to missing data.

13 PROTOCOL VIOLATIONS

A protocol violation occurs when the subject, investigator, or Sponsor fails to adhere to significant protocol requirements affecting the inclusion, exclusion, subject privacy, and primary endpoint criteria. Protocol violations for this study include, but are not limited to, the following:

Failure to meet inclusion/exclusion criteria

Failure to withdraw participant from the intervention arm in a timely fashion when the participant requests voluntary withdrawal from the study.

Failure to comply with Good Clinical Practice (GCP) guidelines will also result in a protocol violation. The Sponsor will determine if a protocol violation will result in withdrawal of a subject.

When a protocol violation occurs, it will be discussed with the investigator and a Protocol Violation Form detailing the violation will be generated. This form will be signed by a Sponsor representative and the Investigator. A copy of the form will be filed in the site's regulatory binder and in the Sponsor's files.

14 DATA SAFETY MONITORING

Not applicable

15 STATISTICAL METHODS AND CONSIDERATIONS

Prior to the analysis of the final study data, a Statistical Analysis Plan (SAP) will be written describing all analyses that will be performed. The SAP will contain any modifications to the analysis plan described below.

15.1 Data Sets Analyzed

All eligible patients who are enrolled in the study will be included in the analysis.

15.2 Demographic and Baseline Characteristics

We will compare several demographic and baseline characteristics between subjects in the intervention and control groups at baseline. These include age, race, and clinical characteristics such as prostate specific antigen.

15.3 Analysis of Primary Endpoint

The primary statistical analysis will compare the probability of correctly responding to the two knowledge survey questions between subjects randomized to the intervention and control sites using logistic regression. The primary predictor of the logistic model will be the binary, site-specific intervention indicator. We will also include site, time and intervention group by time interaction terms. Since randomization by site may not balance, all relevant sociodemographic and clinical characteristics of the subjects may be included in the models; we will also include other factors that are not balanced between the groups. We will assess balance by comparing means of continuous characteristics using two sample t-tests and by comparing categorical characteristics using chi-square tests.

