4 STUDY DESIGN

4.1 Study Overview

This is a four-site, site-randomized, two-period, cluster-crossover design. 160 subjects are planned. Sites will be randomized in pairs to period 1 usual care or intervention. After all sites have met accrual goals, the pairs will cross over to intervention or usual care. In usual care, study participants will complete surveys and prepare for their visit as they usually would, and receive whatever education materials and counseling is normally provided by the sites. We will assess the materials and counseling received by surveying the patients about this. In the intervention, subjects will be contacted by the coordinating site (UCSF) and offered educational materials that include personalized risk estimates, along with coaching to help list questions for their upcoming visit with the urologist.

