5 CRITERIA FOR EVALUATION

5.1 Primary Efficacy Endpoint

The primary endpoint is the proportion of patients who respond accurately to two survey items assessing whether they are more likely to die of prostate cancer or other causes (other causes are more likely); and whether waiting three months to make a treatment decision will affect their survival a lot; somewhat; or a little or not at all (a little or not at all is the correct answer).

Knowledge of these key facts is an important endpoint because patients often associate the word cancer with high mortality risks, and with urgency to act. Patients also often associate more invasive treatment with greater benefit.

In the case of early-stage, low-risk prostate cancer, patients should recognize that early-stage prostate cancer patients are more likely to die of other causes than prostate cancer; and that most can safely take three months to make decisions. This knowledge opens patients up to consideration of active surveillance along with surgery and radiation therapies.

Our intervention aims to educate patients about their (low) mortality risk and the time available for decision-making after their cancer diagnosis **before** they see their urologist for primary treatment counseling. Therefore, we will assess this endpoint just prior to the first urology appointment after a biopsy confirms early-stage low-risk cancer, and compare the usual care results to the intervention arm.

In preliminary studies at an academic medical center with highly educated patients, our intervention increased the proportion of patients responding accurately from 69% to 88%. Meanwhile, at our community sites, 52% of usual care patients responded accurately. We hypothesize that in our randomized controlled trial, we will see over 75% of patients respond accurately in the intervention arm, versus 50% in the usual care arm.

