15.4 Analysis of Secondary Endpoints

The statistical analyses of the secondary endpoints will follow the same regression model approach as with the primary endpoint using a regression model appropriate for the outcome type. For example, we will use linear regression to analyze continuous endpoints such as MaxPC and polytomous logistic regression for categorical endpoints of decision support intervention (DSI) coaching versus usual care.

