15.6 Sample Size and Randomization

We will base sample size calculations on the comparison of the probability of correctly responding to the two survey questions between subjects at the intervention versus control sites with a design effect correction to accommodate the potential correlation of responses within sites [44]. That is, we will inflate the sample sizes resulting from standard sample calculations for the comparison of two proportions by the design effect, $1 + (n-1)*\rho$, where n is the sample size per site and ρ is the intraclass correlation coefficient of the primary binary response[45]. We are interested in detecting an alternative where the probability of the primary response increases from 0.5 in the control sites to 0.75 in the intervention sites. Standard power calculations for chi-square tests to compare two proportions [45] show that tests based on a total sample size of 116 would have power 0.8 to detect the alternative of interest. Since our study design involves 8 clusters (four sites measured in two time periods), our initial design would include 15 subjects measured in each site at each time. Preliminary data indicate that the intraclass correlation coefficient of the primary response is quite low within sites; the estimated intraclass correlation coefficient was less than 0.01. This estimate produces a design effect of 1.14 and we inflate the required number of subjects per site and time to 17 for a total sample size of 136.

Randomization: At baseline, this study will randomize two sites to the intervention and two sites to serve as controls. There are six possible assignments of two intervention and control sites in our study and we will generate a uniform (0,1) random number to select one of them.

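### The intervention-by-time term makes the Section 15.3 primary model rank-deficient (7 columns, rank 6) with fixed site terms and two periods, so under 0/1 coding the coefficient on the named primary predictor is not estimable as written

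*Combined protocol and SAP*

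**What the plan says.** Section 15.3 sets out a logistic regression for the probability of answering both knowledge items correctly. On the treatment term it says: "The primary predictor of the logistic model will be the binary, site-specific intervention indicator". It continues: "We will also include site, time and intervention group by time interaction terms".

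Section 4.1 gives the design: "This is a four-site, site-randomized, two-period, cluster-crossover design". Section 8.1 starts two sites on each arm, and every site then switches. Section 15.6 counts eight clusters, from four sites and two periods, and sizes them accordingly: "we inflate the required number of subjects per site and time to 17 for a total sample size of 136". On clustering it reports that "the estimated intraclass correlation coefficient was less than 0.01".

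The target is a single overall contrast. Section 5.1 expects that "we will see over 75% of patients respond accurately in the intervention arm, versus 50% in the usual care arm", and Section 15.6 uses 0.75 against 0.5.

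Section 15.4 carries the model forward: "The statistical analyses of the secondary endpoints will follow the same regression model approach as with the primary endpoint".

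Section 15.3 does not say whether site is fixed or random, whether time means period or calendar date, how the terms are coded, or which contrast is the primary test. Section 15 promises a separate SAP before the final analysis, but nothing in the documents settles these points.

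**The concern.** In a two-period crossover of whole sites, a site's sequence is a fixed property of that site. The intervention-by-period interaction is the sequence difference in another form, so it competes with the site terms for the same information. If all the listed terms are fitted with fixed sites, the model is over-parameterised, and the coefficient that a reader of Section 15.3 would take as the primary result depends on which redundant column is removed. With random sites the model can be fitted, but under 0/1 coding that coefficient is the effect in period 1 only. It then rests on a between-site comparison and discards the within-site information that the crossover was designed to provide. Either way, the primary estimate would be settled by coding or column order rather than by the plan.

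**Working it through.** **Inputs.** Four sites, two periods, two sites per sequence (Sections 4.1, 8.1); 0.50 versus 0.75, 17 men per site-period, ICC below 0.01 (Section 15.6). Two-sided 0.05 is assumed because no alpha is stated.

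**The plan's sample size reproduces.** n per arm = [1.96·√(2·0.625·0.375) + 0.842·√(0.25 + 0.1875)]² / 0.25² = 57.7, so 58 per arm and 116 in total. The design effect is 1 + 14·0.01 = 1.14; 15·1.14 = 17.1, taken as 17; 17·8 = 136. The assumed alpha is therefore consistent with the plan, and the sample size is not in dispute.

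**Rank.** Let T = intervention and P = period, both 0/1.

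| Sequence | P | T | T×P | T + P − 2·T×P |
|---|---|---|---|---|
| DSI first | 0 | 1 | 0 | 1 |
| DSI first | 1 | 0 | 0 | 1 |
| Usual care first | 0 | 0 | 0 | 0 |
| Usual care first | 1 | 1 | 1 | 0 |

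The last column is the DSI-first indicator, which is a sum of site indicators. Intercept + 3 site terms + period + intervention + interaction = 7 columns, rank 6. This holds for all six allocations that Section 15.6 allows, and adding sites does not help (6 sites: 9 columns, rank 8; 8 sites: 11 columns, rank 10). Reading the interaction as starting-arm group by time, with 0/1 coding, also gives rank 6 and a non-estimable intervention coefficient.

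**What can be estimated.** With fixed sites, only within-site changes (period 2 minus period 1) carry information on the three non-site coefficients:

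- DSI-first sites: βP − βT
- usual-care-first sites: βP + βT + βTP

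That is two equations for three unknowns. Half the difference between them is βT + 0.5·βTP, the period-averaged effect, and it is estimable. βT and βTP separately are not. Under ±1/2 coding the intervention coefficient is this period-averaged effect; the interaction remains non-estimable.

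**Precision of the intended effect.** Information per cell is 17·0.25 = 4.25 (control) and 17·0.1875 = 3.1875 (intervention), with four cells of each. SE = √(1/17 + 1/12.75) = 0.370. Power = Φ(ln 3/0.370 − 1.96) = 0.84. The same value results from dropping the interaction, from ±1/2 coding, and from βT + 0.5·βTP in the full model.

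**If a site term is dropped and the interaction kept.** Take a reference site and a dropped site from opposite sequences, differing by d log-odds. Substituting the identity above moves the intervention coefficient by d, downward or upward according to which sequence holds the reference. Of the 12 reference/dropped pairs, 8 are of this kind: rank 6 of 6, SE 0.640 from the inverse expected information, power Φ(1.0986/0.6395 − 1.96) = 0.40 before any shift. The other 4 pairs come from the same sequence and stay singular (6 columns, rank 5).

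The documents do not give site differences, so d is shown as a range. The site SD on the logit scale is √(ICC·0.25)/0.25, and the SD of a two-site difference is √2 times that.

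| ICC | Site SD | SD of two-site difference | True OR 3.0 reads, for ± the latter |
|---|---|---|---|
| 0.0025 | 0.10 | 0.14 | 2.60 to 3.46 |
| 0.005 | 0.14 | 0.20 | 2.46 to 3.66 |
| 0.01 | 0.20 | 0.28 | 2.26 to 3.98 |

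**If site is random.** The fixed part (intercept, period, intervention, interaction) has full rank 4. Under 0/1 coding the intervention coefficient uses only the four period-1 cells. Its variance is 1/8.5 + 1/6.375 = 0.2745 with no site variance, giving SE 0.524 and power 0.55. At ICC 0.01 (logit variance 0.04) it is 0.2745 + 0.04, giving SE 0.561 and power 0.50.

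**If time is calendar date.** With a continuous calendar term in place of period, the model has rank 7 of 7.

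**The case against.** The strongest reply is that the target itself is sound. Section 15.3 names a predictor, not a coefficient, and opens by comparing response probabilities between intervention and control. That overall contrast is estimable with power 0.84. The difficulty depends on three things that Section 15.3 leaves open: fixed sites, two-level time and 0/1 coding. Calendar time is not fanciful, because Sections 8.1 and 8.2 let each site switch at 20 participants, whereas Section 4.1 has sites switch after all have met their goals. The power of 0.40 needs an analyst to delete a site term and keep the redundant interaction, which is unlikely; the interaction is listed last and most software would drop it. The synopsis also mentions univariate tests, Section 15.6 is powered on a chi-square test, and a later SAP could settle the coding.

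Much of this stands, and it limits the point to an unclear test rather than a lost one. It is also fair to say that under 0/1 coding the interaction is aliased with site, intervention and period jointly, and with site alone only under ± coding. But the remaining readings do not give a clear answer. Random sites yield a period-1 effect under 0/1 coding. With calendar time and an interaction, the 0/1 coefficient is the effect at time zero. The univariate tests do not repair the regression that Section 15.3 calls primary, and the promised SAP is not among the documents.

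**Conclusion.** The concern holds. With fixed site terms and two periods, the Section 15.3 model has rank 6 for 7 columns, the interaction cannot be tested, and under 0/1 coding the primary predictor's coefficient is not estimable. The algebra is exact and does not depend on sample size or on the allocation drawn. The practical size depends on how the redundancy is resolved: no loss (SE 0.370, power 0.84) if the interaction is dropped, against SE 0.640, power 0.40 and a shifted odds ratio in the least favourable handling. With random sites and 0/1 coding, power is 0.50 to 0.55 for a period-1 effect. These figures assume 17 men per site-period, 0.50 versus 0.75, two-sided 0.05 and no design effect.

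This should be fixed before analysis, because the primary test ought not to rest on a software default. For the secondary endpoints it carries over only where the same site-period-arm model is used. Some are measured before and after the visit (Section 5.2), and time there could mean survey time, which is not aliased.

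**What to change.** In Section 15.3, state the primary model as logistic regression on fixed site, period (a site's first or second accrual block) and intervention, with no intervention-by-period term, and name that intervention coefficient as the primary test. Present any intervention-by-period (sequence or carry-over) contrast as descriptive only, from a model without site fixed effects. Use the same specification in Section 15.4 wherever the same site-period-arm model applies. The covariate adjustment in Section 15.3 is not affected by this point.

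The cost is a sentence of protocol or SAP wording. No patients, visits or data change. With fixed sites and two periods nothing estimable is given up. Had random sites or calendar time been intended, the interaction would move from the primary model to a descriptive analysis.

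### The 15.3 model leaves site-by-period variation out of the standard error; at the plan's ICC ceiling the type I error lies between 5.0% and about 7%

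*Combined protocol and SAP*

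**What the plan says.** Section 15.3 makes the binary intervention indicator the main predictor in a logistic model and continues: "We will also include site, time and intervention group by time interaction terms". It does not say whether site is fixed or random. It names no site-by-period effect, no GEE and no cluster-robust variance. Section 15.4 states that the secondary analyses "will follow the same regression model approach as with the primary endpoint".

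Section 15.6 targets a case where "the probability of the primary response increases from 0.5 in the control sites to 0.75 in the intervention sites" and reports that "tests based on a total sample size of 116 would have power 0.8 to detect the alternative of interest". It then allows for clustering: "Since our study design involves 8 clusters (four sites measured in two time periods"), with 15 men in each to begin with. It describes the ICC of the primary response as a within-site quantity estimated at below 0.01. It goes on: "This estimate produces a design effect of 1.14 and we inflate the required number of subjects per site and time to 17", for a total of 136. The synopsis plans 160 enrolled and about 136 evaluable; under 8.1 each site accrues 20 men before it crosses over.

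**The concern.** Sizing and analysis appear to assume different correlation structures. In 15.6 the unit that shares a correlation is one site in one period. In 15.3 men are independent once site and time are in the model.

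Every site contributes men to both arms, so a difference between sites that lasts through both periods cancels out of the comparison. A shift confined to one site in one period does not cancel, because each site-period belongs wholly to one arm. If such shifts exist, the model standard error for the DSI effect is too small and a DSI with no effect would be declared effective too often.

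They are plausible here. Usual-care materials are local (8.3.1) and clinic staff know the assignment (8.2). Section 4.1 has sites cross over after all have met accrual, while 8.2 has each site cross over on reaching its own 20 men; under 8.2 the calendar periods differ by site and one common time term cannot describe them.

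A randomisation test offers no fallback. With the six equally likely assignments in 15.6, its smallest possible p-value is 1/6 = 0.17. The model standard error therefore carries the whole inference.

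**Working it through.** **Inputs.** From 15.6: response 0.50 against 0.75, power 0.8, 8 site-periods, ICC below 0.01 (0.01 used), 15 and then 17 men per site-period. Not in the documents, so assumed: two-sided α = 0.05 (this reproduces the plan's 116; one-sided gives 92); site as fixed terms; time as a two-level period; and *c*, the share of the ICC that is stable across a site's two periods, shown from 0 to 1.

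**The plan's figures.** Two proportions, no continuity correction: 58 per arm, 116 in total, power 0.802. Then 116/8 = 14.5, rounded up to 15; 1 + (15−1)×0.01 = 1.14; 15×1.14 = 17.1, taken as 17; 17×8 = 136. All reproduce. The 15 is the number of men per site-period, although 15.6 defines *n* as the size per site; 30 men per site would have given 1 + 29×0.01 = 1.29.

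**The interaction term.** Let B = 1 for the two sites that start in usual care and 0 otherwise, period = 0 or 1, and DSI = 0 or 1. In all eight site-periods

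DSI × period = (DSI + period + B − 1)/2.

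B and the constant are sums of site indicators, so the interaction adds nothing to site, period and DSI: 7 columns, rank 6. It cannot stand in for site-by-period variation. That leaves 8 − 6 = 2 degrees of freedom of such variation, which the model takes to be zero.

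**Type I error.** With fixed site terms, the ratio of true to model variance is

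R = [1 + (m−1)ρ − mρc] / (1 − ρc), and α = 2[1 − Φ(1.96/√R)].

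For m = 17 and ρ = 0.01, with simulation of the site + period + DSI logistic model (Wald test, 40,000 trials per row):

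| c | R | α, formula | α, simulated |
|---|---|---|---|
| 1 (all stable by site) | (1.16−0.17)/0.99 = 1.00 | 5.0% | 4.9% |
| 0.8 | (1.16−0.136)/0.992 = 1.03 | 5.4% | 5.4% |
| 0.5 | (1.16−0.085)/0.995 = 1.08 | 5.9% | 5.9% |
| 0 (all site-period specific) | 1.16 | 6.9% | 6.9% |

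At c = 0 the standard error is 1 − 1/√1.16 = 7% too small. With 20 men per site-period the c = 0 figure is 7.2% (simulated 7.1%). With ρ = 0.005 and 17 men it is 5.9%.

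Beyond the plan's bound, c = 0 and m = 17 give 8.8% at ρ = 0.02 and 14.4% at ρ = 0.05. With c = 1 the simulated rate stays at 4.9% to 5.2% for every ICC tried.

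**Effect of carrying the design effect into the standard error.** √1.16 = 1.077, so intervals are about 8% wider.

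- Power: 68/1.16 = 58.6 effective men per arm, 0.807 by formula and 0.82 by simulation of the corrected test with c = 0.
- If c = 1: 2[1 − Φ(1.96×1.077)] = 3.5%.
- If c = 0 and ρ = 0.05: 2[1 − Φ(1.96×√(1.16/1.80))] = 12%.

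**Estimating the variance instead.** A site-period analysis on 2 residual degrees of freedom holds type I error at 4.7% to 4.8% (ρ = 0.01, 17 per site-period), but power falls to 37% to 40% at 136 men and 41% to 45% at 160.

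**The case against.** The best defence is that site is in the model and that 15.6 describes its correlation as within sites. If that correlation is stable over both periods, the site terms remove it and the test has its stated size. Inflating the sample for it was then merely cautious. The ICC is also given as below 0.01, so 0.01 is a ceiling. And 15.3 leaves open whether site is fixed or random, while section 15 allows a later SAP to modify the analysis.

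Most of this stands. A reader might infer from the missing term that the type I error definitely exceeds 5%, or that it reaches 9% to 15%. The documents support neither. The first needs part of the ICC to be specific to the site-period, and no such split is given. The second needs ICCs two to five times the stated bound.

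What the defence does not remove is the mismatch. The 1.14 was computed from men per site-period across eight clusters, which fits correlation specific to the site-period; correlation that is purely stable by site would have needed no inflation once site is in the model. Either the inflation was unnecessary or the standard error omits what it was meant to cover, and the plan does not say which.

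A fixed multiplier also has real limits. It is not estimated from the trial, and it over-corrects or under-corrects when its assumption fails. It should therefore be reported with a range of ρ.

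**Conclusion.** The concern holds as a gap of bounded size. Section 15.3 covers correlation that is stable within a site and nothing at the site-by-period level; its interaction term does not help when site is fixed. At the plan's ICC ceiling and 136 evaluable men, type I error is 5.0% at best and about 7% at worst, or 5.9% if the ICC splits evenly. These figures rest on two-sided 5%, fixed site terms and two-level periods. Which end of the range applies cannot be read from the documents.

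**What to change.** In 15.3:

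- Keep the site and period terms, state that site is fixed, and drop the aliased interaction. If it stays, which column the software removes can change what the DSI coefficient estimates.
- Prespecify that the DSI confidence interval and p-value are also reported with the model standard error multiplied by √(1+(m−1)×0.01), where m is the mean number of evaluable men per site-period.
- Repeat with ρ = 0.02 and 0.05 as a sensitivity range. At m = 17 the multipliers are √1.32 = 1.15 and √1.80 = 1.34.
- Claim a robust effect only if it survives the 0.01 correction.
- State the properties: conservative (about 3.5%) if the correlation is stable by site; not fully protective if the site-period ICC is above 0.01; and chosen over estimating the variance on 2 degrees of freedom because that would cut power to about 40%.

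In 15.4, present ρ as an assumed range, because 15.6 gives an ICC for the primary response only.

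The cost is a short paragraph of SAP text, intervals about 8% wider, and power of about 0.81 to 0.82 on a normal reference, still at the planned 0.8. No extra men are needed.
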